9.6 Plans for analyzing the primary objectives: treatment effectiveness (Aim 1)

The primary objective is to compare the proportions of participants in the study arms with 7-day point-prevalence abstinence from cigarettes at 6-months post enrollment. We will define 7-day point-prevalence by saliva cotinine (< 15 ng/ml) or expired air CO (<10 ppm). All participants who report being quit and no NRT or e-cigarette use will be requested to provide saliva samples, expired air CO will be measured in participants who report being quit and report concurrent NRT or e-cigarette use. If a participant is lost to follow-up or does not provide a saliva or CO sample, they will be considered a current smoker. The primary analysis will be performed from an intent-to-treat perspective. Chi-square tests will be used to compare the outcomes between treatment groups. Outcomes will be considered different with  $p<0.01$ .

As a randomized study, it is hoped that the two groups will be balanced between potential confounders. Appropriate comparisons between the groups will be performed (chi-squared tests, t-tests, etc.) to identify any potential confounders that were not balanced. If significant areas of imbalance are identified, logistic regression modelling will be performed to adjust for potential confounding.

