### **Moderators/Mediators of primary interest:**

- Sociodemographics: Sex, age, marital status, race/ethnicity, education level, financial burden, health insurance, internet and smartphone access and modality
- Smoking history: Years smoked, daily smoking rate, other tobacco/nicotine use (e.g., cigars, cigarettes), current/past use of tobacco treatments, nicotine dependence
- Cancer variables: Cancer type, cancer stage, treatment, and days since diagnosis
- Site characteristics: Site, geographic location, clinic volume, baseline organizational readiness, site usual care

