#### 4.6 Stratification Factors

Stratification within site

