### 5.2 Enhanced Usual Care (EUC) (Arm A)

The EUC reflects the NCCN Smoking Cessation Guideline recommendations and mirrors what is often delivered at cancer centers and community settings: assessment of smoking status, provision of quitting advice, and referral to the national NCI Smokers' Quitline for free counseling. Some participating NCORP community sites might provide additional tobacco treatment, which we will assess and document as well.

All participants randomized to EUC will have received the assessment of smoking status and provision of quitting advice through the screening and recruitment (virtual clinician referral) process, and will additionally be referred to the NCI Smoking Quitline (smokefree.gov). Referrals will be sent via email by EASEE PRO automatically upon randomization to the EUC arm see

supplemental Appendix P). Referrals will also be sent via mailed letter (see EUC Referral Letter Supplemental Appendix Z1A) by the MGH study staff to the address provided by EUC participants.

On an ongoing basis, the NCI Quitline will provide reports on participant engagement (date and duration of Quitline call) with quitline services. This interaction will be documented in Rave.

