### 9.2 Power calculation:

#### 9.2.1 Aim 1. Primary effectiveness outcome.

The study will have 80% power to detect a 17% difference in 7-day point-prevalence tobacco abstinence with a two-sided significance level of 0.01 with 280 participants.

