For continuous abstinence, with a sample size of 140 in each arm then smallest detectable difference will be 21% with 80% power and a Bonferroni corrected alpha of 0.002 using and an estimated control rate of 20%.
- 9.2.6 Aim 1. Secondary effectiveness outcome 5.  
For sustained abstinence, with a sample size of 140 in each arm then smallest detectable difference will be 19% with 80% power and a Bonferroni corrected alpha of 0.002 using and an estimated control rate of 13%.
- 9.3 Estimate of drop-outs/loss to follow-up:  
We estimate that 10% of participants will die within 6-months of enrollment, so an additional 10% (n=28) will be recruited.
- 9.4 Total Sample size:  
308 patient participants.
- 9.5 Plans for handling missing data:  
At the outset, we will examine the frequency distributions of all variables. Data from all sites will be pooled for analysis, after confirming there is no significant heterogeneity among sites or adjusting as needed. We will compare the baseline characteristics to assess whether randomization distributed covariates evenly. Outcome analyses will be intent-to-treat; we will classify participants who are lost to follow-up and those who do not provide a saliva or an expired air sample as current smokers. We will determine whether there is differential dropout in the groups and consider developing probability-of-completion weights to obtain unbiased estimates of treatment effect. We will assess whether data are missing at random. We will perform sensitivity analysis using: 1) a complete case analysis and 2) multiple imputation for missing data.

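### Randomization is stratified by site but the primary test is an unstratified chi-square; adjustment for site or covariates hangs on undefined significance checks, and no adjusted result is given a rank

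*Combined protocol and SAP*

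**What the plan says.** Section 4.6 gives one randomization factor: "Stratification within site". Section 9.6 describes an intent-to-treat primary analysis and continues: "Chi-square tests will be used to compare the outcomes between treatment groups. Outcomes will be considered different with" p<0.01. No stratum or site term is named. The sizing in 9.2.1 is an unadjusted two-proportion calculation.

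Site enters the effectiveness comparison only in 9.5, the missing-data section: "Data from all sites will be pooled for analysis, after confirming there is no significant heterogeneity among sites or adjusting as needed". Covariates enter only in the second paragraph of 9.6: "Appropriate comparisons between the groups will be performed (chi-squared tests, t-tests, etc.) to identify any potential confounders that were not balanced". The consequence follows: "If significant areas of imbalance are identified, logistic regression modelling will be performed to adjust for potential confounding". Elsewhere, site and the baseline variables appear as exploratory moderators (2.4 and 9.8.1), which do not feed the primary test.

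The plan expects that sites may differ. Section 5.2 notes: "Some participating NCORP community sites might provide additional tobacco treatment, which we will assess and document as well". The site characteristics listed among the moderators of primary interest in 2.4 are: "Site, geographic location, clinic volume, baseline organizational readiness, site usual care".

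**The concern.** Three things do not fit together.

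- **Design and test.** Patients are balanced by site within arms, but the test ignores site. If quit rates differ between sites, the test uses a variance that is too large for the design and gives up some power.
- **Undefined branches.** The check in 9.5 has no test, threshold or adjustment method, and does not say whether heterogeneity means the quit rate or the treatment effect. The balance check in 9.6 has no variable list and no threshold. Baseline imbalance after proper randomization arises by chance, so a significance test is a poor trigger for adjustment.
- **No rank.** Nothing says whether an adjusted result replaces or only supports the chi-square. If the two fall on opposite sides of 0.01, two analysts could follow the plan and report different conclusions.

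**Working it through.** **1. The plan's own figure.** Section 9.2.1 claims "80% power to detect a 17% difference in 7-day point-prevalence tobacco abstinence with a two-sided significance level of 0.01 with 280 participants". With the unpooled two-proportion formula, rates 0.32 and 0.15 (9.1):

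n per arm = (z0.995 + z0.80)² × [0.32×0.68 + 0.15×0.85] / 0.17² = 11.679 × 0.3451 / 0.0289 = 139.46, rounded up to 140.

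Power at 140 per arm is 0.80184, an exact match to the table. With the pooled variance that a Pearson chi-square uses, power at 140 per arm is 0.787. There is no site term in either calculation.

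**2. Why the chi-square is conservative.** With 1:1 balance within equal sites, the null variance of the difference in proportions is (4/N) × [p̄(1−p̄) − τ²], where τ² is the between-site variance of the quit rate. The chi-square uses (4/N) × p̄(1−p̄). Its true alpha is therefore about 2Φ(−2.576/√(1−f)), with f = τ²/[p̄(1−p̄)].

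Take p̄ = (0.15+0.32)/2 = 0.235, so p̄(1−p̄) = 0.1798, with normal site effects on the log-odds scale:

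- SD 0.5: τ² = 0.0076, f = 0.042, alpha about 0.0085.
- SD 1.2: τ² = 0.0341, f = 0.190, alpha about 0.0042 (many-site limit; slightly higher with 12 sites).

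**3. Simulation.** From the documents: 280 patients, 15% versus 32%, two-sided 0.01, and roughly 308/25 = 12.3 sites (5.1.2; 3.1 gives a minimum of 11). Assumed: the site SDs, the site sizes, and 1:1 balance within site through permuted blocks of 4. Overall rates are held at 15% and 32% (23.5% in both arms under the null). No continuity correction. Monte Carlo SE is about 0.2 points for power and 0.00035 for type I error at 40,000 and 80,000 runs; the discordance column used 20,000.

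Twelve equal sites:

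| Site SD | Power chi-square / CMH | Gain (points) | Type I error chi-square / CMH | Opposite sides of 0.01 at the planned effect |
|---|---|---|---|---|
| 0 | 0.794 / 0.791 | −0.3 | 0.010 / 0.010 | 0.8% |
| 0.5 | 0.800 / 0.811 | +1.1 | 0.0086 / 0.0097 | 1.5% |
| 0.8 | 0.804 / 0.833 | +2.9 | 0.0072 / 0.0099 | 3.1% |
| 1.2 | 0.809 / 0.868 | +5.9 | 0.0049 / 0.0095 | 6.3% |

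Many small uneven sites, with sites under 4 patients pooled. At SD 0, power is 0.795/0.786 (40 sites), 0.791/0.782 (60) and 0.794/0.786 (80), a loss of 0.8 to 0.9 points. At SD 0.5 the gain is 0.2 to 0.7 points; at SD 1.2 it is 4.5 to 5.3 points.

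**4. If 9.5 is followed.** Suppose the heterogeneity check is a 5% Pearson test of site by outcome, followed by CMH when it fires. With 12 equal sites it fires in 46%, 84% and 97% of trials at SD 0.5, 0.8 and 1.2. Power of check-then-CMH against always CMH is 0.811/0.812, 0.834/0.834 and 0.866/0.866, with type I error 0.009 to 0.010.

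**5. The baseline trigger.** With k independent variables tested at an assumed 0.05, the chance of at least one significant imbalance in properly randomized arms is 1 − 0.95^k: 40% for k = 10 and 64% for k = 20.

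**6. False positives from an open choice.** Taking whichever of chi-square and CMH is significant gives type I error of at most 0.0104. Taking the best of chi-square, CMH and a triggered logistic model (15 to 20 assumed covariates, 15,000 null runs per setting) gives about 0.012, against 0.009 to 0.011 for the chi-square alone.

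**The case against.** The best defence is that the deciding test is effectively named. In 9.6 the intent-to-treat statement, the chi-square and the 0.01 criterion stand together, the criterion is attached to no other test, and the sizing is unadjusted. That stands. A reader might infer that the plan has no primary test; it does. What stays open is 9.5, which makes pooling itself conditional, and the missing rank of any adjusted result.

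Second, the larger power losses do not describe a plan in which 9.5 is carried out. That also stands: step 4 shows that an ordinary check followed by CMH recovers almost all of the gain. The loss applies if the chi-square decides regardless.

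Third, the larger SDs are wide. With a 15% overall control rate, SD 0.8 implies site quit rates of about 3% to 41% (95% range), and SD 1.2 about 1% to 55%. Counselling and nicotine replacement supply are centralised and the referral is standardised, which argues for smaller differences. At SD 0.5 or below the gain is about 1 point or less, and with 40 to 80 small sites CMH can lose slightly. This limits the size of the point but does not remove it.

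Fourth, some of the differing site terms come from staff procedures: 3.1 concerns staff enrolment and 6.3.1 a rostering survey. True, but 5.1.2 sets patient accrual by subcomponent site, 4.5 registers institution and affiliate, and 4.6 says only site. The unit still needs stating.

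**Conclusion.** The point holds as a recommended clarification with a modest gain. The primary test ignores the only stratification factor, and the routes to adjustment are undefined and unranked. The chi-square remains valid: true alpha is about 0.009 at SD 0.5 and 0.005 at SD 1.2, for a nominal 0.01. If it decides, a stratified test would give about 1, 3 or 6 more power points at SD 0.5, 0.8 or 1.2, the last under very wide site differences. If sites are alike, the stratified test costs 0.2 to 0.4 points at 11 to 20 sites and up to about 0.9 with many small uneven ones. All of this rests on assumed site SDs, site sizes and 1:1 balance within site.

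Two stronger readings are not supported. A reader might infer that ignoring site inflates false positives. It does the opposite, and choosing between chi-square and CMH adds essentially nothing; the open covariate choice may add a very small amount. A reader might also infer that the sample size is wrong. The stated 140 per arm reproduces exactly, and N need not change on this account.

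**What to change.** Make these changes in 9.5 and 9.6 before any outcome data are seen:

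- Name one deciding test: a CMH test stratified by the site unit used in randomization, two-sided 0.01. State the unit.
- Pool small sites by a rule based only on randomized counts, for example all sites with fewer than 4 patients as one stratum.
- Report the Mantel-Haenszel risk difference with a 99% confidence interval. Keep the unstratified chi-square as a sensitivity analysis.
- Remove the significance tests of site heterogeneity and baseline balance as triggers for adjustment. Keep the baseline table descriptive.
- State that any covariate-adjusted logistic model is supportive and cannot overturn the primary result, with baseline covariates fixed in advance. One option is a conditional logistic model with site as the stratum and either the Heaviness of Smoking Index or daily smoking rate. Do not use both, because the index already contains cigarettes per day. That is 2 slopes (arm and covariate) against about 280 × 0.235 = 66 expected quits.

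The cost is plan wording and minor programming, with no new data and no change in N, plus the small power loss given above if sites turn out alike. If the sponsor prefers to keep the chi-square as the deciding test, one sentence saying so, and ranking every adjusted result below it, would close the gap in rank but not recover the power.

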9.7 Plans for analyzing the secondary objectives: secondary treatment effectiveness (Aim 1)

The 5 secondary objectives (defined in Section 2.3) include various ways of measuring abstinence at different times of assessment. In order to adjust for multiple comparisons, differences will be considered significant at  $0.01/N=0.01/5=0.002$  level.

Similar to the primary objective is to compare the proportions of participants in the study arms with 7-day point-prevalence abstinence from cigarettes at 3-months post enrollment. We will define 7-day point-prevalence by saliva cotinine (< 15 ng/ml) or expired air CO (< 10 ppm). All participants who report being quit and no NRT or e-cigarette use will be requested to provide saliva samples, expired air CO will be measured in participants who report being quit and report concurrent NRT or e-cigarette use. If a participant is lost to follow-up or does not provide a saliva or CO sample, they will be considered a current smoker. Chi-square tests will be used to compare the outcomes between treatment groups.

Another secondary objective is to compare the proportions of participants in the study arms that self-report cigarette abstinence at 3-months. The participant will be asked, "In the past 7 days, have you smoked a cigarette, even a puff." With the answer recorded as "Yes" or "No". If the self-report response is unavailable, the participant will be considered a current smoker. Chi-square tests will be used to compare the outcomes between treatment groups. The process will be repeated using self-reported cigarette abstinence at 6-months.

Another secondary objective is to compare the proportions of participants in the study arms that report a continuous abstinence at 6 months. The participants will be asked, "How long has it been since you last smoked a cigarette (even one or two puffs)?" at 6 months. If the response is more than or equal to 3 months (e.g. time since previous survey), the participant will be considered having a continuous abstinence at 6 months. If the self-report response is unavailable, the participant will be considered not having a continuous abstinence at 6 months. Chi-square tests will be used to compare the outcomes between treatment groups.

Another secondary objective is to compare the proportions of participants with sustained abstinence at 6 months. To qualify as a sustained abstinence at 6 months, the participant must qualify as biochemically-verified 7-day point prevalence cigarette abstinence at 3 and 6 months, using the definition above. If either measure is not available the participant will not be considered sustained abstinence at 6 months. Chi-square tests will be used to compare the outcomes between treatment groups.

Generalized Estimating Equations (GEE) approach will be used to study the treatment effect over time, incorporating 3 & 6 month follow-up data. This will take into account the repeated measures structure of observations within the same individuals over time and allow for analysis of incomplete data across time.

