### 2.3 Secondary Objectives:

#### 2.3.1 Secondary treatment effectiveness (Aim 1)

Secondary smoking outcomes (5) include:

- Biochemically-verified 7-day point prevalence abstinence at 3-months follow-up
- Self-reported 7-day point prevalence cigarette abstinence at 3- and 6-months follow-up

- Significant reduction (> 50% reduction in reported number of cigarettes per day) in daily smoking from baseline to 3- and baseline to 6-months follow-up
- Continuous (no self-reported smoking since last survey point) and sustained abstinence at 6 months (cotinine-verified at 3-months and 6-months)

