#### **Numeric Results for Testing Two Proportions using the Z-Test with Unpooled Variance**

H0:  $P1 - P2 = 0$ . H1:  $P1 - P2 = D1 \neq 0$ .

Target	Actual	Diff						
		Power	Power* N1	N2	N	P1	P2	D1
0.80	0.80400	117	117	234	0.2700	0.1000	0.1700	0.0100
0.90	0.90042	148	148	296	0.2700	0.1000	0.1700	0.0100
0.80	0.80014	78	78	156	0.2700	0.1000	0.1700	0.0500
0.90	0.90167	105	105	210	0.2700	0.1000	0.1700	0.0500
0.80	0.80045	126	126	252	0.2900	0.1200	0.1700	0.0100
0.90	0.90130	161	161	322	0.2900	0.1200	0.1700	0.0100
0.80	0.80185	85	85	170	0.2900	0.1200	0.1700	0.0500
0.90	0.90186	114	114	228	0.2900	0.1200	0.1700	0.0500
0.80	0.80184	140	140	280	0.3200	0.1500	0.1700	0.0100
0.90	0.90061	178	178	356	0.3200	0.1500	0.1700	0.0100
0.80	0.80115	94	94	188	0.3200	0.1500	0.1700	0.0500
0.90	0.90119	126	126	252	0.3200	0.1500	0.1700	0.0500
0.80	0.80095	148	148	296	0.3400	0.1700	0.1700	0.0100
0.90	0.90146	189	189	378	0.3400	0.1700	0.1700	0.0100
0.80	0.80289	100	100	200	0.3400	0.1700	0.1700	0.0500
0.90	0.90024	133	133	266	0.3400	0.1700	0.1700	0.0500
0.80	0.80043	159	159	318	0.3700	0.2000	0.1700	0.0100
0.90	0.90101	203	203	406	0.3700	0.2000	0.1700	0.0100
0.80	0.80088	107	107	214	0.3700	0.2000	0.1700	0.0500
0.90	0.90015	143	143	286	0.3700	0.2000	0.1700	0.0500

\* Power was computed using the normal approximation method.

- 9.2.2 Aim 1. Secondary effectiveness outcome 1.  
For biochemically-confirmed 7-day point prevalence abstinence at 3-months, with a sample size of 140 in each arm then smallest detectable difference will be 18% with 80% power and a Bonferroni corrected alpha of 0.002 using and an estimated control rate of 20%.
- 9.2.3 Aim 1. Secondary effectiveness outcome 2.  
For self-reported 7-day point prevalence abstinence at 6-months, with a sample size of 140 in each arm then smallest detectable difference will be 22% with 80% power and a Bonferroni corrected alpha of 0.002 using and an estimated control rate of 31%.
- 9.2.4 Aim 1. Secondary effectiveness outcome 3.  
For self-reported 7-day point prevalence abstinence at 3-months, with a sample size of 140 in each arm then smallest detectable difference will be 22% with 80% power and a Bonferroni corrected alpha of 0.002 using and an estimated control rate of 28%.
- 9.2.5 Aim 1. Secondary effectiveness outcome 4.  

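### The flat 0.002 threshold for the secondary outcomes is valid, but Holm's step-down at 0.01 gives the same error control, never rejects less, and costs one sentence

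*Combined protocol and SAP*

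**What the plan says.** Section 9.7 sets the rule for the secondary outcomes: "In order to adjust for multiple comparisons, differences will be considered significant at" 0.01 divided by 5, that is 0.002. It then describes five comparisons: verified abstinence at 3 months, self-reported abstinence at 3 and at 6 months, continuous abstinence, and sustained abstinence. For each, "Chi-square tests will be used to compare the outcomes between treatment groups". No step-down or other stepwise rule appears.

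Sections 9.2.2 to 9.2.6 use the same level. Section 9.2.2, for example, gives a detectable difference of 18% "with 80% power and a Bonferroni corrected alpha of 0.002 using and an estimated control rate of 20" per cent, with 140 per arm.

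The primary outcome is tested separately, at a "two-sided significance level of 0.01 with 280 participants", and this point does not touch it.

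Section 2.3.1 introduces the family with "Secondary smoking outcomes (5) include", but its list also contains "Significant reduction (> 50% reduction in reported number of cigarettes per day) in daily smoking from baseline to 3- and baseline to 6-months follow-up". That item has no test in 9.7 and no power statement in 9.2.

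**The concern.** The five outcomes are different readings of abstinence in the same patients, and sustained abstinence is by definition a subset of verified abstinence at 3 months. A treatment that works should tend to move them together. In that situation a flat Bonferroni threshold gives up power that a step-down rule would keep at the same family-wise error. At stake is how many secondary outcomes can be declared significant if the intervention works broadly. The validity of the secondary claims is not at stake.

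**Working it through.** **1. The plan's threshold.** 0.01/5 = 0.002 reproduces. Five tests at 0.002 have a family-wise error of at most 5 × 0.002 = 0.01, and 0.00996 if independent.

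**2. Holm's rule.** Order the p-values p(1) ≤ … ≤ p(5). Compare p(k) with 0.01/(6 − k) and stop at the first failure. The steps are 0.002, 0.0025, 0.00333, 0.005 and 0.01. If m₀ null hypotheses are true, the first one wrongly rejected faces a threshold of at most 0.01/m₀, so the error is at most m₀ × 0.01/m₀ = 0.01 under any dependence. The first step equals the Bonferroni level and later steps are looser. Holm therefore never rejects less, and it cannot create a first rejection.

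**3. The plan's power figures.** The table in 9.2 is headed "Numeric Results for Testing Two Proportions using the Z-Test with Unpooled Variance". Power = Φ(d/SE − z), with SE = √{[p₁(1 − p₁) + p₂(1 − p₂)]/n}. The secondary tests are taken as two-sided, which the plan does not state.

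- Primary, 32% against 15%, n = 140, alpha 0.01: SE = √[(0.2176 + 0.1275)/140] = 0.0497, and Φ(3.424 − 2.576) = 0.802. The plan gives 0.80184, so the formula is the right one.
- 9.2.2, 20% control, 18 points, alpha 0.002: SE = √[(0.2356 + 0.16)/140] = 0.0532, and Φ(3.386 − 3.090) = 0.616, not 0.80. The difference with 80% power is 21.1%. At alpha 0.01 it would be 18.2%.
- 9.2.5, with the same control rate, n, power and alpha, states 21%, and power there is 79.7%. Sections 9.2.2 and 9.2.5 therefore disagree on identical inputs, and 9.2.5 is the one that reproduces.
- 9.2.3, 9.2.4 and 9.2.6 give 76.9%, 78.3% and 79.4%. The detectable difference for 9.2.3 is 22.6% against a stated 22%.

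**4. Gain from Holm.** Correlated binary outcomes were simulated with a Gaussian copula, the plan's control rates (20, 31, 28, 20, 13%) and pooled two-proportion tests, 20,000 trials per row. The latent correlation of 0.7 is an assumption, because the documents give none. The size 154 per arm is 308/2. Mean power is over the outcomes with a real effect. Separate runs differ by about a point.

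| True effects | n per arm | Mean power, Bonferroni → Holm | All five significant | At least one significant |
|---|---|---|---|---|
| 17 points on all five | 154 | 58% → 66% | 21% → 41% | 91% both |
| 17 points on all five | 140 | 52% → 60% | 16% → 34% | 87% both |
| Differences stated in 9.2.2–9.2.6 | 140 | 73% → 81% | 38% → 61% | 97% both |
| 12 points on all five | 154 | 24% → 28% | 3% → 9% | 58% both |
| 10 points on all five | 154 | 14% → 16% | 1% → 3% | 40% both |
| 17 points on three | 154 | 53% → 55% | – | 79% both |
| 17 points on two | 154 | 54% → 56% | – | 72% both |
| 17 points on one | 154 | 59% → 59% | – | 60% both |

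With 17 points on all five and 140 per arm, correlations of 0.5 and 0.85 also give mean gains of 8 to 9 points.

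**5. Size of the family.** Counted by time point, 2.3 lists 1 verified + 2 self-reported + 2 reduction + 2 (continuous, sustained) = 7. Seven tests at 0.002 would sum to 0.014. A family of seven starts at 0.01/7 = 0.0014 under either method.

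**The case against.** Bonferroni is named in advance, computed correctly and carried unchanged from 9.2 into 9.7. A conservative rule for secondary outcomes is a legitimate choice. It gives each outcome a fixed threshold that does not depend on the other p-values, and simultaneous intervals that match the tests are easy to form. Holm's benefit also rests on scenarios the plan does not state. The 17-point effect belongs to the primary outcome, and for the secondary outcomes the plan gives detectable differences, not expected effects. Some larger uniform effects are not even coherent with the plan: 20 points on sustained abstinence would be 13% + 20 = 33%, above the 32% assumed for verified abstinence at 6 months, which bounds it.

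All of this stands, and it limits the point to an efficiency gain. It does not remove the gain. Section 9.7 specifies significance decisions only and plans no simultaneous intervals, so the plan as written does not use the flat rule's main advantage.

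A reader might infer that the trial loses power on all five outcomes and misses real effects for nothing. The documents do not support that. The loss appears only when several effects are real, the flat rule does buy simplicity, and no conclusion drawn under it would be invalid.

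**Conclusion.** This is a worthwhile improvement, not an error. Holm at family level 0.01 dominates the flat 0.002 as a testing rule, and that holds whatever the correlation. The size of the benefit is conditional. It is about 8 points of mean power per outcome if all five effects lie at 17 to 22 points, about 2 points at 10 points on all five, about 1 to 3 points if two or three effects of 17 points are real, and none if only one is. The chance of at least one significant secondary outcome is the same under both rules. The power figures rest on the plan's control rates, an assumed latent correlation of 0.7 and two-sided tests.

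Two matters in the same text are firmer and have to be settled with it: the 18% in 9.2.2 does not fit alpha 0.002, and the number of tests in the family is unclear.

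**What to change.** Before outcome data are seen:

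- In 2.3 and 9.7, fix the list of secondary tests. State whether the two smoking-reduction measures belong to the family; if they do, give them a test.
- In 9.7, replace the flat 0.002 by Holm's step-down at family level 0.01 over that list.
- Report Holm-adjusted p-values with unadjusted confidence intervals, labelled as unadjusted.
- In 9.2.2, correct the detectable difference to about 21% at alpha 0.002, then present 9.2.2 to 9.2.6 as first-step (least favourable) figures. If the family is not five, recompute them all at the new first step.

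The cost is one sentence in 9.7 and a correction in 9.2, with no more patients and no change to the primary test. The downside is that simultaneous intervals matching Holm's decisions are less simple, and the unadjusted ones can disagree with the adjusted p-values. A sponsor who values matching intervals more than the power may keep Bonferroni, but should then say so and still settle the family and 9.2.2.
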